## 14.0 Withdrawal of Subjects

14.1 Anticipated circumstances under which subjects will be withdrawn from the research without their consent include instances of repeated missed appointments, apparent intoxication upon arrival to study visits,

inappropriate behavior of any kind toward staff on our team, or similar circumstances. Participants arriving to appointments intoxicated may be rescheduled or may be terminated from the study, with this decision made by the primary researcher on this protocol.

- 14.2 Participants who choose to withdraw from the study may do so for any reason without penalty to them and will be paid for their participation to that point. During the informed consent process, the choice of participants to be in research or to stop participating at any time is explained verbally and in written form on a bulleted consent document. It is imperative that patients do not feel pressure to participate and understand the study is voluntary. The participant may discontinue participation at any time without penalty or loss of benefits to which the subject is otherwise entitled.

## **15.0 Risks to Subjects**

- 15.1 Study procedures pose minimal risks. The bulleted consent form and informed consent process describes foreseeable risks and discomforts to the participants because of being in this study.
- 15.2 Potential risks to human subjects participating in the proposed research are minimal and include as follows:
  - Breach of confidentiality.
  - Psychological discomfort from answering questions about lifestyle behaviors such as diet, exercise, and alcohol intake.
  - Physical risks associated with blood draw procedures including and not limited to pain or discomfort, venipuncture, or fainting.
  - Physical or emotional risks associated with liver screening and receiving liver-health feedback.
  - Risk of coercion.
- 15.3 N/A, procedures which may have unforeseeable risks are not expected.
- 15.4 N/A, pregnant persons are excluded from the research study.
- 15.5 N/A, risks to others who are not subjects are not expected.

## **16.0 Potential Benefits to Subjects**

- 16.1 Free, noninvasive liver screening and brief behavioral intervention has potential to reduce risks of liver biopsy and other invasive assessments or interventions in the context of progressive liver damage, thereby reducing the participant's health risks and discomforts, which is a potential benefit.
- 16.2 Individual participants are unlikely to have any other direct benefits of being in this study.

## **17.0 Data Management and Confidentiality**

- 17.1 Plans for analyzing the data will be included on clinicaltrials.gov following established timelines and requirements set by the National Institutes of Health. Piloting procedures in randomized clinical trials serves many valuable functions including gauging feasibility of recruitment, piloting randomization procedures, comparing intervention-specific retention rates,

withdrawal rates including reasons for withdrawal, and intervention-specific fidelity rates. A CONSORT diagram will describe the screening and enrollment process implemented and demonstrate feasibility. To examine the acceptability of SBIRT/P procedures, quantitative and qualitative measures of satisfaction with Fibroscan® screening and of the brief motivational intervention will be analyzed.

- 17.2 Multiple protections will be implemented to secure the data and minimize risk of breach of confidentiality, including (a) training and authorization of access: limiting access to personally identifiable information to personnel with appropriate and up to date human subjects training who are supervised by the investigative team and reminded to keep information confidential, (b) password protection and encryption: digital and hard-copy data securely in accordance with data integrity standards using Brown CIS-vetted and approved software and servers, (c) physical controls and separating identifiers and data: storing personally identifiable information separately from data or biological specimens in locked locations designated for this purpose and coded with a unique ID number that is not directly associated with the participant (e.g., not a birth date), (d) certificate of confidentiality: explaining during informed consent verbally and in writing that the study has obtained a certificate of confidentiality (CoC) from the National Institutes of Health, as well as informing potential participants verbally and in writing during informed consent about the limitations of confidentiality including the limitations of the CoC and instructing participants to protect their own information.
- 17.3 Procedures that will be used for quality control of collected data will include working from highly detailed project manuals and standard operating procedures that are followed with line-by-line checks for all procedures. The project coordinator or team member in a similar supervisory role will review hard-copy data for errors and document digitally or in writing that this oversight was conducted including the date and name of the person conducting the check.
- 17.4 Data and specimens will be banked for future use following best-practice guidelines to ensure integrity and confidentiality of the samples.
  - Once collected, specimens will be stored at our designated laboratory space at Brown SPH until they are used for research purposes or discarded.
  - The specimens will be accessed by primary members of the research team and core lab staff.
  - Future use may involve sending the specimens to clinical and/or research laboratories outside Brown for the purpose of performing further testing, assays, or similar functions.
  - The data to be stored with each specimen include study ID number, date of collection, and visit number, where applicable. No personal identifying information is stored with study specimens under any circumstances.
  - The specimens will remain under the control of the researchers and will not be released to outside parties.

## **18.0 Provisions to Monitor the Data to Ensure the Safety of Subjects**

18.1 N/A. This section is not required when research does not involve more than minimal risk to participants.

## **19.0 Provisions to Protect the Privacy Interests of Subjects**

19.1 All interviews, exams, and sessions will be conducted following applicable human subjects research protections privacy standards including conducting these in a manner and space that ensures privacy and confidentiality of information. Private identifiable information associated with research data will be available only to research personnel who have been trained in human subjects' protection guidelines and are certified by the Collaborative Institutional Training Initiative (CITI) as mandated by the Brown University IRB. Deidentified data will be indexed by numeric codes which are sequentially generated numbers that are not derived from private identifiable information.

19.2 CEHC is an active clinic serving uninsured individuals as described in other relevant sections herein. The CEHC employs Patient navigators, i.e., Navegantes, who are trained community health workers assisting with patient care and outreach for CEHC. Navegantes are key to the success of this research, as they are a trustworthy and familiar presence in the clinic. Navegantes will assist with a warm hand-off where applicable, i.e., from clinic staff to research staff. Participants are informed that they have the right to decline to answer a particular question that feels too uncomfortable. By conducting study procedures in a more familiar setting (i.e., CEHC), the goal is to increase participants' comfort and sense of agency.

19.3 The research team will access information about the participant via the medical record, the participant's self-report, biometric measurements, and laboratory and clinical tests collected to complete the study aims. Only primary members of the research team are permitted to access participant research data following the required standards to uphold data integrity.

## **20.0 Compensation for Research-Related Injury**

20.1 N/A. The research does not involve more than minimal risk, and there is not available compensation in the event of research-related injury.

## **21.0 Economic Burden to Subjects**

21.1 N/A. Participants are not expected to be responsible for any costs involved in their participation in the research.

## **22.0 Consent Process**

22.1 The informed consent process will adhere to the procedures described in HRP-090-SOP.

22.2 The process for informing potential participants about the study and obtaining their consent for participation will take place in person in a private space and will be documented in writing using a bulleted consent form that is signed with a digital or wet signature by study participants and witnessed by staff on our team.

- 22.3 After the procedures are described to the potential participant, they may take time to think it over prior to signing. If the potential participant remains interested after having time to consider the research, we will make them an appointment to continue.
- 22.4 Ongoing consent is supported through informing participants that participation is voluntary at each study visit.

### ***Non-English Speaking Subjects***

- All study procedures may be implemented in either Spanish or English. Prescreening questions include asking whether the potential participant can read Spanish or English. Those who cannot speak either of these languages will not be eligible to complete informed consent for research participation and cannot enroll in this study. Participants must speak, read, and understand, Spanish or English to be eligible.
- For monolingual Spanish speakers, all procedures and materials will be supplied in Spanish. For participants who are bilingual and prefer procedures implemented in Spanish, all study procedures and materials will be supplied in Spanish.
- Where feasible, self-report, validated measures are sourced from published versions or translated professionally (e.g., Language connections or similar professional service). Bulleted consent forms, advertisements, and other lengthy forms or study materials that would be costly to have professionally translate are translated by a native Spanish speaker who is a member of our research team and reviewed for clarity by a second native Spanish speaker.

## **23.0 Process to Document Consent in Writing**

- 23.1 Informed consent documentation will adhere to the procedures described in HRP-091-SOP using a bulleted consent form with digital or wet signature from the potential participant witnessed by a trained staff member.

## **24.0 Setting**

- 24.1 The settings where we will conduct the research include Clínica Esperanza/Hope Clinic (CEHC) at [name], with the capability to conduct study visits at our primary offices at Brown University SPH [name], as well. Our team also has the capacity to reach potential participants through digital and community outreach.
- 24.2 CEHC was founded in 2007 as a place for patients, volunteers, community partners, and donors to be healthy. CEHC's community health care model ensures that quality care comes from caregivers who are fully integrated in the community. Our partnership between Brown University and CEHC teams will enable us to reach the target underserved population at risk for MetALD.
- 24.3 CEHC focuses on providing high-quality, culturally attuned, and linguistically appropriate healthcare to all uninsured adults in Rhode Island. CEHC's patient base is primarily made up of Spanish-speaking, Latinx

immigrants from Central and South American countries. CEHC has a core paid staff and a robust network of volunteer medical providers, nurses, medical interpreters, and non-provider volunteers. More than 4,000 patients across nearly 7,000 visits are served annually. CEHC has recently expanded their space, now occupying three suites in the [name] location where recruitment will take place.

- 24.4 CEHC serves a diverse population with significant unmet healthcare needs, including those with alcohol intake and overweight or obesity placing them at increased risk of MetALD. Of CEHC's current patient population, 92% are Latinx, primarily from Central and South America, and 90% are Spanish speaking. Many patients experience immigration-related stress. Many also face instrumental barriers to care, with 4 out of 5 patients living well below the poverty line. More information can be found on CEHC's website, [www.aplacetobehealthy.org](http://www.aplacetobehealthy.org).
- 24.5 CEHC is paid through a consultancy for this funded research project. Appropriately compensating clinical partners is best practice for community engagement. CEHC's consultancy fee, approved by their organization, Brown University, and the National Institute of General Medical Sciences, accommodates the use of CEHC resources, including supplies, space, and staff time. Patient navigators, i.e., Navegantes, are trained community health workers assisting with patient care and outreach for CEHC. The assistance of Navegantes with participant recruitment and retention is key to the success of this research. Seamless integration into clinic operations and culturally appropriate approaches are key to successfully reaching underresourced communities.

## 25.0 Resources Available

- 25.1 There are ample resources available to conduct the research. Data showing the number and demographics of the patient population served by the CEHC provides evidence for the feasibility of recruiting the designated 40 randomized participants within the timeframe expected. The CEHC serves over 4,000 patients over 7,000 visits annually. Patients commonly have indications of cardiometabolic disease, e.g., hypertension (59%), diabetes (41%), and hyperlipidemia (22%). The CEHC has integrated the AUDIT-C screening tool into their clinical procedures, allowing the research team to identify prospective participants based on BMI and alcohol use. Therefore, this study should meet or exceed the goal of recruiting 1 or 2 participants per week to obtain a final sample of 40 randomized participants in the limited project period. Moreover, the research team is fully prepared to expand recruitment through community or digital outreach and conduct study procedures at our Brown SPH laboratory should it be necessary to meet enrollment targets.
- 25.2 The research team includes experienced members in multiple roles (e.g., research assistants, project coordinator, medical laboratory technician, faculty investigators, licensed practitioners, interventionists) contributing effort to the project at our partnering sites, in team meetings, in our laboratory, and in related preparations and efforts. The combined effort devoted to this project for the research team triples the project period or more, indicating a very high level of effort committed by the team.

25.3 The research team from Brown will be partnering primarily with the clinical facility described above, the Clínica Esperanza/Hope Clinic (CEHC), which occupies three suites in fully remodeled space in the Olneyville neighborhood in the city of Providence. The CEHC is a highly active clinic providing holistic care including primary medical care, specialty clinics, and related services (e.g., food pantry, community clothing closet) to adults without insurance in Rhode Island. The CEHC has earned the Gold Standard of Care from the National Association of Free and Charitable Clinics and has earned the highest levels of financial transparency awarded to charitable organizations. The Brown SPH facilities occupy three office floors of the [name], where our research team has offices, cubicles, meeting spaces, laboratory space, and usage of the third-floor laboratory preparation room.

25.4 In case of emergency, emergency medical services (EMS) will be called. Participants found to be experiencing medical or physical events that do not require emergency medical services will be evaluated by the study physician or another medical provider at partnering clinical sites or at Brown. An advantage of conducting the study activities at the partnering site is the wealth of clinic and medical staff available to assist in the event of a medical or physical event. In any case, the participant will be encouraged to seek medical care as appropriate.

25.5 In case of an emergency psychiatric event that presents imminent risk of harm to the participant or others, emergency medical services (EMS) will be called. Any participant who is found to be experiencing a psychiatric or psychological issue that is of concern and possible imminent risk will be evaluated by [name], a licensed clinical psychologist in Rhode Island, or one of several other licensed clinicians on the team.

25.6 The target population at risk for MetALD is also at risk for known or emergent medical issues or events that are not likely to be due to participation in the minimal risk research study. These include but are not limited to events such as hospitalization due to an alcohol-related injury or detoxification from alcohol, hypertension or heart palpitations, or emergencies related to medical events or accidents.

25.7 Processes to ensure that all persons assisting with the research are adequately informed are as follows:

- All team members complete thorough training on the protocol and procedures consistent with their duties on the project. Team members complete CITI training prior to research engagement as well as EHS biosafety training where indicated.
- Weekly team meetings, or more frequent meetings at some stages of training and data collection, ensure that staff are closely supervised and obtain a high level of proficiency.
- Individuals conducting the Fibroscan® are trained operators certified by Echosens, the manufacturer of our Fibroscan® ultrasound machine. Individual Fibroscan® results are reviewed by a study physician who will instruct the team on appropriate next steps and referrals.

- Sessions with the study counselor are audio-recorded with sections selected at random for review and coded by supervisors to ensure fidelity to the intervention protocol. Interventionists are supervised at a minimum biweekly and typically weekly and are given feedback on adherence to the protocol.

STATISTICAL ANALYSIS PLAN

PROJECT TITLE:

Team Science to Identify and Intervene on Metabolism- and Alcohol-Associated Liver Disease (MetALD)

PRINCIPAL INVESTIGATOR:

[name] [name]
Center for Alcohol & Addiction Studies
Center for Addiction & Disease Risk Exacerbation
[contact]
[contact]

DATE OF PLAN:

July 27, 2024

To establish feasibility and acceptability of community-based screening for MetALD, a CONSORT flow diagram reflecting participants' progress through our screening and enrollment process will be created, including the number and percentage of individuals screened for self-reported weight and alcohol-use co-factors who were eligible for noninvasive liver screening (primary outcome measure) and the proportion of those eligible who agreed to non-invasive liver screening (primary outcome measure). These findings will inform how many individuals encountered through our proposed community recruitment efforts exhibit key biobehavioral co-factors for MetALD, the feasibility of reaching them in future studies and the feasibility of conducting noninvasive liver screening with them. To examine the acceptability of noninvasive liver screening, we will assess participant satisfaction with FibroScan® on a 100-point visual analogue scale following baseline procedures (primary outcome measure).

To test whether personalized feedback reduces alcohol-associated risk for MetALD, residualized multiple linear regression analyses will test whether participants receiving the enhanced intervention with personalized FibroScan® feedback report fewer heavy drinking days, fewer drinks per week, and more alcohol-free days than participants receiving the standard intervention (secondary outcome measure). Age, sex, ethnicity, and variables reflecting baseline levels of outcomes will be specified as a priori covariates. Including participants' baseline levels of outcomes will increase precision of the test of condition on follow-up outcomes and thus enhance statistical power. While not powered to test whether biological sex (assigned at birth) moderates the intervention, we will test for main effects of sex on outcomes and explore pre and post means separately by sex. The same approach will be utilized for ethnicity and age group. We will evaluate the residual distributions of drinking summary scores to ensure model assumptions are met. If the residual distributions do not approximate multivariate normal distributions, we will utilize appropriate other approaches. For example, we can pivot to evaluate standard drinks via a count regression model (e.g., negative binomial distribution). As another example, we can pivot to evaluate heavy-drinking days as complete absence of any heavy drinking vs. 1+ heavy drinking day via a logistic regression model (e.g., binary distribution).

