## 4.0 Study Endpoints

- 4.1 Primary endpoints include: (a) proportion screened who have alcohol intake and weight-related risks for MetALD; (b) proportion eligible and invited to participate who agree to noninvasive liver imaging with Fibroscan® and arrive for their scheduled appointment; (c) satisfaction with Fibroscan® liver screening; and (d) acceptability metrics for SBIRT/P overall, including retention rates and satisfaction ratings compared across randomized conditions. Satisfaction with Fibroscan liver screening is assessed with a single-item visual analog scale with 0 indicating low satisfaction and 100 indicating high satisfaction. Satisfaction with SBIRT/P overall is assessed with the Client Satisfaction Questionnaire, provided in an attachment.
- 4.2 Secondary endpoints include: (a) self-reported drinking quantity and frequency (e.g., heavy drinking days, drinks per week, alcohol-free days); (b) phosphatidylethanol (PEth), a direct alcohol metabolite biomarker; (c) self-reported weight-related behaviors (e.g., diet quality, eating dysregulation, food cravings, and physical activity); and (d) weight-related biometrics (e.g., body weight, waist circumference, blood pressure). Descriptions and items for secondary-endpoint measures are provided in an attachment. Measures to describe the sample participating in this research, to account for important covariates, and to facilitate team science are also attached. The battery of measures is streamlined from prior projects to reduce staff time, minimize participant burden, and facilitate remote data collection.
- 4.3 Exploratory endpoints include plasma biomarkers to comprise a preliminary panel to screen for likely steatosis and fibrosis in patients at risk for MetALD, with Fibroscan® as a reference standard. These include plasma biomarkers of microbial translocation, innate immune activation, obesity-related metabolic dysfunction, and liver fibrosis.

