Interested volunteers who would like to participate in screening, appear potentially eligible, and complete informed consent with written documentation continue with screening that day, or, if necessary, are scheduled for a visit as soon as possible. Eligibility criteria assessed include interviews, weight-related biometrics, and blood tests, including tests for Hepatitis B and C which are common exclusionary preexisting liver diseases in this population. Additional measures include culturally validated assessments of diet and lifestyle behaviors, described in attachments.

- 6.4 Those eligible are scheduled for two appointments: (1) a randomization visit typically completed within 5 to 10 business days of in-person screening, and (2) a followup visit ~30 days later. Attendance at all visits is facilitated by reminders in multimethod formats, including email, text message, phone call, and/or calendar invitations, complying with the participant's preferences. The first visit includes the Fibroscan® liver screening, biobehavioral assessments, interviews, and a brief conversation with our study counselor (~45 minutes to 1 hour) to build motivation for lifestyle change. The followup visit repeats biobehavioral assessments and interviews and includes a brief check-in (~15 minutes) with our study counselor with an exit interview assessing satisfaction with study procedures and barriers to change. The Fibroscan® liver screening is not repeated at followup. For participants who are monolingual Spanish speakers or bilingual and prefer to complete the study in Spanish, all procedures including the brief intervention will be implemented in Spanish by bilingual personnel who are either native Spanish speakers or have documented professional Spanish fluency. The total study duration for individual participants is typically less than 45 days, with some variability to allow for flexibility in scheduling.

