## **12.0 Local Number of Subjects**

12.1 This pilot aims to randomize 40 participants to standard (n=20) and enhanced (n=20) conditions, with randomization stratified by relevant study variables.

12.2 It is anticipated that ~80 interested volunteers may complete informed consent prior to in-person screening to confirm eligibility, allowing for ineligibility and disinterest after screening.

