- 13.4 Patients who may be suitable for the study and who have visits scheduled in advance may be sent a letter informing them that Brown University is recruiting patients in the clinic for a research study. In clinic, patients are invited by their health provider, patient navigator, or Brown University research team member to answer a limited set of prescreening questions to see if the study may be suitable for them. Prescreening questions are in plain language, with many asked in an easy to answer yes/no format. For example, "Are you able to read English or Spanish?" The pre-screening questions and corresponding semi-structured script are provided in an attachment. Potential participants who complete pre-screening may be offered a nominal gift (e.g., a pen, notepad, water bottle) or meal as a gesture of appreciation, consistent with best practices for community engaged research.
- 13.5 If patients are unable to participate in the prescreening at the time of their clinic appointment, prescreening can be completed over the phone or deferred until their next clinic visit. In this case, permission would be requested to remind the patient of their upcoming appointment by common methods (e.g., phone, mail). Potential participants who hear about the study by word of mouth or advertisements in the community or online may also contact the study team by phone, text, or online to hear more about the study and answer the pre-screening questions. In the case of digital outreach with online prescreening, Brown-approved survey software (e.g., Qualtrics or similar) will be used and will include a study landing page that provides enough information to describe study procedures to allow potential participants to decide about their interest in continuing with prescreening. Questions used for online prescreening are the same as those provided in the attachment for phone prescreening and also include the AUDIT-C 3-item alcohol screening measure.
- 13.6 Following pre-screening, participants will continue with informed consent for research participation prior to further screening to confirm eligibility. This last stage of screening includes a blood draw for quantification of liver function and cardiometabolic factors using standard clinical liver, metabolic, and lipid panels, HbA1c, and Hep B/C testing if not already performed (see

Exclusion criteria), as well as a timeline followback interview to assess recent alcohol consumption with high precision.

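### The protocol counts agreement plus arrival for the Fibroscan among those eligible and invited as primary endpoint (b); the SAP counts agreement alone among those eligible, and neither fixes the stage of eligibility.

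*SAP*

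**What the plan says.** Protocol section 4.1 lists, as primary endpoint (b), the "proportion eligible and invited to participate who agree to noninvasive liver imaging with Fibroscan® and arrive for their scheduled appointment". The numerator has two conditions, agreement and arrival, and the denominator has two, eligibility and invitation.

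The SAP's opening paragraph, on feasibility and acceptability, gives as primary "the proportion of those eligible who agreed to non-invasive liver screening (primary outcome measure"). The same sentence has just introduced "individuals screened for self-reported weight and alcohol-use co-factors who were eligible for noninvasive liver screening", which is the natural antecedent of those eligible. Invitation and arrival do not appear.

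The protocol also sets the order of events. Section 13.6 says that after pre-screening "participants will continue with informed consent for research participation prior to further screening to confirm eligibility". Section 6.3 describes that further screening as interviews, biometrics and "blood tests, including tests for Hepatitis B and C which are common exclusionary preexisting liver diseases in this population". Under section 6.4, those eligible are scheduled for "a randomization visit typically completed within 5 to 10 business days of in-person screening", and "The first visit includes the Fibroscan® liver screening". Section 12.2 plans for about 80 consenting and section 12.1 for 40 randomised, the difference "allowing for ineligibility and disinterest after screening".

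**The concern.** Feasibility is what this pilot measures, and (b) is the endpoint that says whether people offered a liver scan go on to have one. Two current documents define it differently in the numerator and in the denominator. Neither refers to the other for the definition, and neither says at which point in the screening sequence a person becomes eligible for (b).

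If the definitions stay as they are, the analyst must choose between them, possibly after seeing the counts. A reader planning the next study could also take an agreement rate for a scan-uptake rate.

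**Working it through.** The documents state no target, precision or expected value for (b), so there is no figure to reproduce. The check sets the two definitions side by side and then asks what each would yield.

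**Definitions**

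| | Protocol 4.1(b) | SAP |
|---|---|---|
| Numerator | agreed and arrived | agreed |
| Denominator | eligible and invited | eligible |
| Stage of eligibility | not stated | not stated |

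**Step 1: common denominator.** Let N be the denominator, A the number who agreed, and a = P(arrive | agreed).
- SAP = A/N and protocol = (A × a)/N.
- Ratio = 1/a and gap = (A/N) × (1 − a).

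The documents give no value for a. With assumed counts N = 100 and A = 80, the SAP figure is 80% throughout:

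| Assumed a | Arrived | Protocol figure | Gap (points) | Ratio |
|---|---|---|---|---|
| 0.95 | 76 | 76% | 4 | 1.05 |
| 0.90 | 72 | 72% | 8 | 1.11 |
| 0.80 | 64 | 64% | 16 | 1.25 |
| 0.70 | 56 | 56% | 24 | 1.43 |

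**Step 2: different denominators.** Let E be the number eligible and I the number of those invited, with everyone who agrees coming from the invited.
- SAP = A/E and protocol = (A × a)/I, so SAP/protocol = (I/E)/a.
- The SAP figure is the higher one only if the share invited exceeds the share of agreers who arrive.

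Assumed counts: E = 120, I = 100, A = 80, arrived = 72. Then SAP = 80/120 = 67% and protocol = 72/100 = 72%. Here I/E = 0.83 is below a = 0.90, and the order reverses.

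**Step 3: stage of eligibility.** Take the planned 80 consenting and 40 randomised (sections 12.1 and 12.2). Assume that consent counts as agreement, that the 40 randomised are exactly those who arrive, that 100 people are eligible at pre-screening, and that all of them are invited.
- SAP wording, eligibility at pre-screening: 80/100 = 80%.
- Protocol wording, eligibility at pre-screening: 40/100 = 40%.
- Protocol wording, eligibility confirmed in person, with F screen failures among the 80: 40/(80 − F).

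| Assumed F | 0 | 10 | 20 | 30 | 40 |
|---|---|---|---|---|---|
| 40/(80 − F) | 50% | 57% | 67% | 80% | 100% |

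If the number eligible at pre-screening is instead varied from 90 to 160, the SAP figure runs from 89% to 50% and agreed-and-arrived on the same base from 44% to 25%.

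Mixing stages can give an impossible result. With F = 20, all 80 who agreed over the 60 confirmed eligible is 80/60 = 133%. The stage must therefore apply to numerator and denominator alike.

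**The case against.** The strongest reply is that little practical harm follows. No test, sample size or go/no-go rule depends on (b), and both documents promise a CONSORT diagram. The scan takes place at the randomization visit, whose attendance is an ordinary entry in such a diagram, so a reader could probably rebuild something close to agreed-and-arrived. That stands, and it limits the weight of the point. It does not settle which proportion will be reported as primary: the SAP attaches that label to agreement and nowhere to attendance at the scan.

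Three stronger readings are tempting, and the documents do not support them.
- **That the SAP counts as eligible anyone who qualifies on self-report.** This is a fair inference from the sentence, but self-reported describes the co-factors people are screened for. The SAP does not say that self-report alone decides eligibility.
- **That the SAP definition inflates uptake.** This holds only on a common denominator. Step 2 shows that it can reverse if some eligible people are not invited.
- **That agreement would be close to 100% by construction if eligible meant confirmed eligible, because everyone would already have consented.** Section 12.2 expects some loss of interest after screening, so people confirmed eligible may still decline the scan visit.

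**Conclusion.** The mismatch is real and explicit in current text. The numerators differ (agreed against agreed and arrived), the denominators differ (eligible against eligible and invited), and the stage of eligibility is open in both documents. Because consent comes before confirmation and the scan visit is typically 5 to 10 business days after in-person screening, the two rules can give different values for the same primary endpoint.

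On a common denominator the SAP figure equals or exceeds the protocol figure by 1/P(arrive | agreed), and the two match only if everyone who agrees arrives. Otherwise the direction is not determined. The size is unknown. A reader might take 40 out of 80 as an arrival rate, but that planning ratio mixes screen failure with loss of interest. Every percentage in steps 1 to 3 rests on assumed counts and shows only how the definitions behave. This is worth fixing, but it is a matter of reconciling a descriptive endpoint and does not threaten the trial's conclusions.

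**What to change.** Reconcile the protocol and SAP to one definition of (b); either document may be amended. The preferred form is the number who agreed and arrived for the Fibroscan, divided by the number eligible and invited. State the stage at which eligibility is judged and apply it to numerator and denominator alike.

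In the CONSORT diagram, report invited, agreed, failed in-person screening, and attended the scan visit as separate counts, so that ineligibility is not read as refusal or non-arrival. An exact 95% confidence interval for the proportion is optional.

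The cost is wording in one or both documents and a few counts. The number invited has to be recorded, which the SAP's description of the diagram does not currently mention. Reported uptake may be lower than an agreement rate. If eligibility is fixed at pre-screening, in-person screen failures will count as not scanned, which is why they need their own line.
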